5. RATIONALE AND BACKGROUND

Xyntha Solofuse prefilled syringe was approved on March 31, 2014 in Korea. The Xyntha Solofuse prefilled syringe is administered by intravenous infusion after reconstitution of the freeze-dried powder with the diluent (0.9% Sodium Chloride). This drug consists of the identical ingredients with the previous Xyntha injection, and the drug and the diluent are supplied within the prefilled dual-chamber syringe. As required for all new drugs approved by the Ministry of Food and Drug Safety (MFDS), information on the safety and efficacy of the new drug should be provided based on the study conducted with at least 600 study subjects who are administered this drug in the setting of routine practice for 4 years from the approval date (March 31, 2014 - March 30, 2018). This non-interventional post-marketing surveillance (PMS) study is an obligation to the MFDS. However, it is expected that about 95 subjects who received this drug should be recruited and registered as study subjects. Considering the number of subjects who meet the analysis exclusion criteria, safety and efficacy information for at least 86 subjects will be collected for all subjects who received this drug during the study period. Background information on Xyntha Solofuse prefilled syringe can be obtained from the current version of the local product document, which is the single reference safety document (SRSD) for information relating to the Xyntha Solofuse prefilled syringe in this study.

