7.5. Study Size

The calculation of sample size is not applicable for this study. At least 600 study subjects will be enrolled in this study to meet the MFDS requirements. In this study, 14 sites conduct complete enumeration study data collection for more than 86 subjects who administered this drug during study period .

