7.7. Data Analysis

7.7.1. Evaluation parameters

1) Case parameters

- Descriptive analysis will be performed regarding the total number of collected CRFs, the number of safety evaluation subjects, the number of efficacy evaluation subjects, the number of discontinued cases and their reasons.

2) Safety parameters

- Safety parameters will be evaluated.
- The incidence of adverse events sorted by body organ and disease/symptom
- If the data is adequate, sub-analysis can be performed for each factor that is considered to affect safety.
- Clinically significant abnormalities found in laboratory tests (if conducted)

3) Efficacy variables

- On-demand treatment
 - Responses to all the injection of the Xyntha Solofuse prefilled syringe used to treat bleeding (4 point scale: excellent, good, moderate, and no response)
 - Number of observations of less than expected therapeutic effect (LETE) (LETE: “no response” rated after each infusion of 2 consecutive infusions within 24 hours after on-demand treatment)
 - In case of bleeding: The number of infusions of Xyntha Solofuse prefilled syringes used to treat each new bleeding episode is rated.
 - Mean infusion dosage
- Prophylactic Therapy
 - Percentage of the study subjects who have experienced bleeding (overall, spontaneous)
 - Annualized bleeding rates (ABRs)
 - Number of observations of less than expected therapeutic effect (LETE)

(LETE: Atypical bleeding occurring within 48 hours after administration of the Xyntha Solofuse Prefilled Syringe by dosage for the prevention of bleeding (spontaneous/at traumatic))

- Mean infusion dosage
- Total factor consumption
- If the data are adequate, sub-analysis can be performed for each factor that is considered to affect the efficacy.

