2.4. Sample size Considerations

The calculation of sample size is not applicable for this study. At least 600 study subjects will be enrolled in this study to meet the MFDS requirements. Although 600 is the assigned number of study subjects, the number of cases will be adjusted considering the actual number of enrolled subjects after the study start day.

Statistical Analysis Plan for rPMS

3. Analysis Populations

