 - Not related to this medicinal product:
 - IV. Unlikely
- 3) Occurrence status of adverse event by demographics and baseline characteristics
- Occurrence status of adverse events will be presented in frequency and percentage and incidence proportion with 95% confidence interval based on categorical variables of demography and baseline characteristics of the patients (sex, age group, past/present disease status, renal/hepatic disorder status). To identify statistically significant difference in occurrence of adverse events among demography and baseline characteristics, Chi-square test or Fisher's exact test will be performed.
- 4) Occurrence status of adverse event by concomitant treatment/therapy
- Occurrence of adverse events will be presented in frequency and percentage and incidence proportion of adverse events with 95% confidence interval by concomitant treatment status and concomitant therapy status. To identify statistically significant difference in occurrence of adverse events among concomitant treatment status, concomitant therapy status, Chi-square test or Fisher's exact test will be performed.
- 5) Analysis of factors that affect safety
- Logistic regression analysis will be performed and an odds ratio with 95% confidence interval will be presented to identify the factors that affect occurrence of adverse events in demography and baseline characteristics (sex, age group, past/present disease status, renal/hepatic disorder status), or concomitant treatment status, concomitant therapy status, etc.

Statistical Analysis Plan for rPMS

- 6) Test of difference for laboratory data before and after administration.
Laboratory data before and after administration will be presented by descriptive statistics and test of difference for laboratory data before and after administration will be performed by using paired t-test (or Wilcoxon signed-rank test). This analysis will be performed if possible.
- 7) Distribution for special patient populations (children (age<19), elderly (age≥65), renal disorder, hepatic disorder, pregnant woman) will be presented. Also, adverse events and adverse drug reactions collected by these groups will be presented in incidence proportion and number events of it for each SOC and PT.

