4) Overall efficacy assessment will be classified as effective/not-effective as follows, presented in frequency and percentage of it.

- ① On-demand treatment

- [Effective]: Subjects with whom the best responses 'Excellent' or 'Good' or 'Moderate'.
- [Not-effective]: Subjects with whom the best responses 'No response'.

- ② Prophylactic Therapy

- [Effective]: Subjects who haven't experienced any atypical bleeding within 48 hours after administration of the Xyntha Solofuse Prefilled Syringe.
- [Not-effective]: Subjects who have experienced at least once atypical bleeding within 48 hours after administration of the Xyntha Solofuse Prefilled Syringe.

5) Efficacy assessment by demographics and baseline characteristics

Classified overall assessment (effective/not-effective) will be presented in frequency and percentage based on categorical variables of demography and baseline characteristics (sex, age group, past/present disease status, renal/hepatic disorder status). To identify statistically significant difference of frequency distribution of classified overall assessment (effective/not-effective) among demography and baseline characteristics, Chi-square test or Fisher's exact

Statistical Analysis Plan for rPMS

test will be performed.

- 6) Efficacy assessment by concomitant treatment (Concomitant Treatments/Therapy status)
Classified overall assessment (effective/not-effective) will be presented in frequency and percentage for concomitant treatment status (Concomitant Treatments/Therapy status). To identify statistically significant difference of frequency distribution of classified overall assessment (effective/not-effective) among concomitant treatment status, concomitant therapy status, Chi-square test or Fisher's exact test will be performed.
- 7) Analysis of factors that affect efficacy
Logistic regression analysis of multivariate analysis will be performed and presented an odds ratio with 95% confidence interval to identify the factors that affect classified overall assessment (effective/not-effective) in demography and baseline characteristics of the patients (sex, age group, past/present disease status, renal/hepatic disorder status), or concomitant treatment status, concomitant therapy status, etc.

7. Reporting Principles

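### SAP 6.6(5) and 6.7(7) commit to logistic regression on factors worth 9 to 11 slopes for about 86 subjects, with no adequacy condition and no sparse-data rule; at low event rates at least one odds ratio will usually be non-finite.

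*SAP*

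**What the plan says.** SAP 6.6(5), on factors that affect safety: "Logistic regression analysis will be performed and an odds ratio with 95% confidence interval will be presented". The candidates are sex, age group, past/present disease status, renal/hepatic disorder status, concomitant treatment status and concomitant therapy status, followed by an open-ended et cetera. This item does not say whether the factors enter one model together or one at a time.

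SAP 6.7(7), on factors that affect efficacy, lists the same candidates and is explicit: "Logistic regression analysis of multivariate analysis will be performed and presented an odds ratio with 95% confidence interval".

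SAP 6.1 fixes sex at two levels and age at five bands.

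Protocol 7.7.1 makes this kind of analysis optional: "If the data is adequate, sub-analysis can be performed for each factor that is considered to affect safety". It says the same for efficacy, and 7.7.2 makes statistical analysis beyond description conditional in the same way. SAP 6.6(5) and 6.7(7) carry no such condition, although the next safety item, 6.6(6), is to be done only if possible.

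On size, Protocol 5 says that "it is expected that about 95 subjects who received this drug should be recruited and registered as study subjects" and that "safety and efficacy information for at least 86 subjects will be collected". SAP 2.4 says: "Although 600 is the assigned number of study subjects, the number of cases will be adjusted considering the actual number of enrolled subjects". Protocol 7.5 adds: "The calculation of sample size is not applicable for this study". Neither document gives an expected adverse event rate, not-effective rate, sex distribution or covariate prevalence.

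**The concern.** The regressions are stated as firm commitments, with many terms and few subjects. The SAP gives no minimum event count, no rule for choosing or merging terms, and no penalised or exact alternative. When a category contains no events, or only events, the maximum-likelihood odds ratio for that term is zero or infinite. Standard software then prints a very large or very small estimate with a Wald interval and p-value that mean nothing. Under the SAP these figures would be tabulated as factors affecting safety or efficacy, in a report required by the regulator. Even where all estimates are finite, a model with so few events per term gives unstable odds ratios that tend to be too extreme.

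**Working it through.** The documents contain no event count, power figure or model size to reproduce, so the check starts from the SAP's own categories.

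**1. Parameter count (SAP 6.1, 6.3, 6.6(5), 6.7(7)).** Sex 1 + age 4 + past/present disease 1 or 2 + renal/hepatic disorder 1 or 2 + concomitant treatment 1 + concomitant therapy 1 = 9 to 11 slopes, before the et cetera.

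**2. Ceiling on events per slope (no assumed rate).** Among 86 subjects the smaller outcome class holds at most 86/2 = 43.
- 43/11 = 3.9 and 43/9 = 4.8 events per slope at best.
- If all 95 expected recruits were analysed, the ceiling would be 47/11 = 4.3 to 47/9 = 5.2.
- At an assumed 10% rate: 8.6 events, so 8.6/11 = 0.8 to 8.6/9 = 1.0 per slope.
- At the 600 subjects still named in the SAP, the ceiling would be 300/11 = 27 to 300/9 = 33.

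**3. Full model: how often is at least one odds ratio non-finite?** Data were simulated with n = 86 and 400 data sets per scenario. The outcome was independent of all covariates, constant columns were dropped, and complete or quasi-complete separation was detected by linear programming. The assumptions, none of them in the documents, were: 0 to 50% female; age bands even or skewed young; binary factors balanced, moderately common or rare; paired items combined or split. Simulation standard error is at most 0.025 per scenario.

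| Event (or not-effective) rate | Separation, all scenarios | Separation, 2% female |
|---|---|---|
| 5% | 0.94–1.00 | 0.98–1.00 |
| 10% | 0.61–1.00 | 0.87–1.00 |
| 20% | 0.10–0.97 | 0.65–0.97 |
| 30% | 0.01–0.89 | 0.47–0.89 |
| 50% | 0.00–0.84 | 0.42–0.84 |

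At n = 600 (60 data sets per scenario) the ranges were 0.00–0.88 at a 5% rate and 0.00–0.20 at 20%.

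**4. Age alone, in case 6.6(5) means one factor at a time.** A band of expected size m has no events with probability (1 − r)^m at event rate r. Treating bands as independent and fixed at expected size, the chance that at least one is empty of events is 1 − Π[1 − (1 − r)^m].
- Even bands, m = 86/5 = 17.2, r = 10%: 0.9^17.2 = 0.163, so 1 − 0.837^5 = 0.59.
- Skewed mix 50/20/15/10/5%, m = 43, 17.2, 12.9, 8.6, 4.3, r = 10%: the empty-band probabilities are 0.011, 0.163, 0.257, 0.404 and 0.636, so 1 − (0.989 × 0.837 × 0.743 × 0.596 × 0.364) = 0.87.
- At r = 20% the same formula gives 0.10 (even) and 0.51 (skewed).

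Simulation with random band sizes gives 0.62 and 0.88 at 10%, and 0.14 and 0.58 at 20%. The five age bands alone are therefore enough to cause the problem at low rates.

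**5. Sex.** If exactly one subject is female, she either has the event or does not. Either way one cell of the sex-by-outcome table is zero, so the sex odds ratio is non-finite at every event rate, in a univariable or a multivariable model.

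**6. Efficacy outcome.** SAP 6.7(4) counts an on-demand subject as not effective only if the best response is no response, so a single moderate rating makes the subject effective. That definition pushes failures towards rarity. Prophylaxis has a different definition, so separate models may be needed, each on a smaller sample. At an assumed n = 43 and a 10% failure rate, separation occurred in 99% of simulated data sets.

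**The case against.** The strongest reply has five parts.

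- **Wording.** A reader might infer that the SAP requires a multivariable safety model. It does not say so: 6.6(5) joins its factor groups with an or and may mean single-factor models. Only 6.7(7) is explicit. This stands, but step 4 shows that single-factor models do not escape the problem.
- **Strength.** A reader might also infer that maximum-likelihood odds ratios will usually not exist whatever the data. The documents do not support that, since they give no rates or covariate mixes. With even age bands, balanced binary factors, and sex constant or balanced, separation falls to 0.10–0.18 at a 20% rate and 0.01–0.03 at 30%. Nor is the whole model lost: under quasi-separation only the affected odds ratios are non-finite. This stands and limits the point to low rates or unbalanced covariates. Likewise, a nearly all-male sample is plausible but is not stated in either document.
- **Count.** SAP 6.3 treats renal/hepatic status as one yes/no item, which favours 9 or 10 slopes over 11. This stands; the range is carried throughout.
- **Existing provisions.** The protocol's adequacy condition, the SAP's promise to adjust case numbers to enrolment, the promise in SAP 5.1 to report method changes, and the planned chi-square or Fisher tests all soften the consequence. None of them tells the analyst when the regression should be dropped, reduced or penalised.
- **Stakes.** These are exploratory analyses in a descriptive study, and detection of inhibitors, the primary objective, does not depend on them. This is fair and limits the weight of the point, but not the need for a rule.

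**Conclusion.** The concern holds in a conditional form. A full model on 9 to 11 slopes with about 86 subjects is overfitted at any event rate. That follows from the ceiling of 3.9 to 4.8 events per slope, judged against the common rule of thumb of 5 to 10, which is a convention and not a figure in the documents. At event or not-effective rates of about 10% or less, at least one odds ratio will usually be non-finite (about 60 to 100% of simulated data sets). At 20 to 30% the answer turns on the covariate mix, and the remaining odds ratios may be finite. The defect in the plan is the missing rule: the SAP commits to the analysis without the protocol's condition and without a sparse-data provision. It should be corrected before database lock, as a matter of secondary analyses only.

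**What to change.** Amend SAP 6.6(5) and 6.7(7) as follows:

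1. Restore the protocol's condition that the data be adequate.
2. State whether 6.6(5) is multivariable.
3. Limit the number of parameters by the number of subjects in the smaller outcome class. One slope per 5 to 10 would be an example: 43 events would then allow 4 to 8 slopes, and 8.6 events about one.
4. Omit sex when it is constant or nearly so.
5. Merge sparse age bands by a rule set without reference to outcome. The under-19 cut-off in SAP 3.3 defines a special population and need not be the modelling split.
6. Fit by Firth penalised likelihood with profile-likelihood intervals (FIRTH option in PROC LOGISTIC; SAS is already the planned software).
7. If the limit in item 3 is not met, report only the cross-tabulations already planned, with Fisher's exact tests.

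The cost is a few sentences of SAP text and one software option. The price is fewer factors examined and slightly shrunken odds ratios; at a low event rate, item 7 may well be what is reported.

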2.1. Objectives

This study aims to observe the safety and efficacy of the Xyntha Solofuse prefilled syringe in the setting of routine practice. The primary objective is to detect medically significant events (factor VIII inhibitor). The secondary objective is to observe the overall efficacy and safety of the Xyntha Solofuse prefilled syringe including serious adverse events.

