2.3.2. Exclusion Criteria

Patients who satisfy the following criteria are not included in the study according to the local labeling:

- 1) Patients who have a history of hypersensitivity to the Xyntha Solofuse prefilled syringe or the ingredients of this drug.
- 2) Patients who have a history of hypersensitivity to hamster proteins.
- 3) Patients who have bleeding disorders other than hemophilia A.
- 4) Patients who have a history of FVIII inhibitors, or currently have or are suspected of having FVIII inhibitors. In case inhibitor titers quantified in Bethesda Units in the laboratory test results are within the normal laboratory range or at least 0.6 BU/mL. If laboratory tests cannot be performed, the investigator will determine whether or not inhibitors exist based on the clinical assessment results that show a decrease in efficacy of the replacement of FVIII (e.g. bleeding at least once, if the replacement of anti-bleeding agents is needed to be administered, and if frequency or dosage of replacement FVIII therapy needs to be increased).
- 5) Use of immunomodulatory therapy (e.g. intravenous injection of immunoglobulin, use of regular systemic corticosteroids, cyclosporine, and mediators of anti-TNF- α).

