4.6. Safety Endpoints

- 1) The incidence and number with 95% confidence Interval for all adverse events/adverse drug reactions investigated within 6 months from initial administration after at least 1 dose of Xyntha solofuse prefilled syringe (If the study subject has not completed the 6-month treatment, relevant data should be collected based on the medical records within the 30 days after the last administration of the drug)

- ① Severity
- ② Action taken
- ③ Seriousness
- ④ Outcome
- ⑤ Causality assessment

2) Laboratory Test

- ① Blood test(Hemoglobin, Hematocrit, RBC, WBC, Platelet Count, ESR, CRP)
- ② Biochemical test(AST(SGOT), ALT(SGPT), ALP, BUN, Creatinine, Factor VIII Inhibition Factor Hemoglobin)
- ③ Urine examination(Protein/Albumin, Glucose/Sugar, Hemoglobin/Blood)

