5.1. Analysis Principles

Statistical analysis will be conducted after database is locked and performed using SAS software version 9.4 according to this statistical analysis plan. If statistical analysis methods are changed, it will be described in the final study report.

Continuous variables will be summarized by the descriptive statistics (n, mean, median, SD (standard deviation), minimum, and maximum). Categorical variables will be presented in the frequency distribution table (n, %).

In case of statistical hypothesis testing, two-sided test will be conducted under 5% significance level and the p-value of each test result will be presented in the summary table.

6. Statistical Analyses

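### The before/after test that the SAP applies to all laboratory data is uninformative for a new factor VIII inhibitor, the event named in the primary objective

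*SAP*

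**What the plan says.** SAP 2.1 gives the aim: "The primary objective is to detect medically significant events (factor VIII inhibitor".

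SAP 4.6, item 2 lists the laboratory data. The biochemistry line reads "Biochemical test(AST(SGOT), ALT(SGPT), ALP, BUN, Creatinine, Factor VIII Inhibition Factor Hemoglobin". The last label is garbled, but Protocol 7.2.5.1, item 6 says that the biochemistry test includes inhibitors, so I take it to contain the inhibitor assay. A further line is "Urine examination(Protein/Albumin, Glucose/Sugar, Hemoglobin/Blood", with no measurement scale stated.

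SAP 6.6, item 6 plans descriptive statistics for laboratory data before and after administration and adds that a "test of difference for laboratory data before and after administration will be performed by using paired t-test (or Wilcoxon signed-rank test". No analyte is exempted. There is no rule for choosing between the two tests or for handling zero differences. The item closes with "This analysis will be performed if possible". Under SAP 5.1, where hypotheses are tested, a "two-sided test will be conducted under 5% significance level", and the p-value of each test goes into the summary table.

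SAP 2.3.2, item 4 excludes "Patients who have a history of FVIII inhibitors, or currently have or are suspected of having FVIII inhibitors".

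Protocol 7.7.2.1 is narrower than the SAP. It allows pairwise comparison or description, if necessary and if the data suffice, for clinically significant laboratory abnormalities that were reported as adverse events.

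**The concern.** A new inhibitor is a rare yes/no event in an individual. The paired t-test asks whether the average changed, and the signed-rank test asks whether changes lean in one direction across subjects. When almost everyone starts negative and stays negative, neither question is the one in the primary objective.

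As written, the rule would put a non-significant p-value beside the inhibitor row when one subject, or several, had developed an inhibitor. A reader of the table could take that as reassurance. The risk is greater because no SAP item defines inhibitor development as an endpoint with its own numerator and a denominator of subjects tested.

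**Working it through.** The documents give no p-value, power or calculated sample size for this test, so there is no figure of theirs to reproduce.

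**Inputs**
- Number of pairs: 86, assumed. Protocol 5 gives at least 86 as the number of subjects with safety and efficacy information. The number with inhibitor results both before and after dosing is not given and may be smaller, because Protocol 7.3.2.4 makes testing optional.
- All other differences exactly zero: assumed, following the exclusion of subjects with inhibitors.
- Two-sided 5% level: SAP 5.1.
- Titres: illustrative assumptions, from 0.6 BU/mL (the figure in the exclusion criterion) upwards.

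**One new inhibitor, paired t-test.** Let one difference be x and the other n − 1 be zero. The mean is x/n and the SD is x/√n, so the standard error is x/n and t = (x/n)/(x/n) = 1. The titre cancels: 0.6, 5 and 500 BU/mL all give t = 1. On n − 1 degrees of freedom, p = 0.320 at n = 86, 0.323 at n = 43, 0.326 at n = 30 and 0.343 at n = 10.

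**One new inhibitor, Wilcoxon.** With zeros dropped, one pair remains and the exact two-sided p is 1.0. The normal approximation gives 0.317.

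**Several new inhibitors at n = 86.** For k equal titres, t = √(k(n − 1)/(n − k)). For k same-sign non-zero pairs, the exact Wilcoxon p is min(1, 2/2^k).

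| k | t | t-test p | Wilcoxon p |
|---|---|---|---|
| 1 | 1.00 | 0.320 | 1.0 |
| 2 | √(170/84) = 1.42 | 0.159 | 0.50 |
| 3 | √(255/83) = 1.75 | 0.083 | 0.25 |
| 4 | √(340/82) = 2.04 | 0.045 | 0.125 |
| 5 | √(425/81) = 2.29 | 0.024 | 0.0625 |
| 6 | √(510/80) = 2.52 | 0.013 | 0.031 |

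The Wilcoxon test first falls below 0.05 at six cases, which is 6/86 = 7.0%. Unequal titres weaken the t-test, because the largest titre inflates the SD: five cases at 1, 2, 4, 10 and 100 BU/mL give p = 0.247.

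**If the other changes are not exactly zero.** The other 85 differences were simulated with an assumed SD of 0.05 to 0.2 BU/mL, with one new case at 0.6 to 50 BU/mL. The fixed values above no longer hold: the median t-test p is 0.32 to 0.52 and the median Wilcoxon p about 0.5. The share of runs with p < 0.05 is about 0 to 5% (t-test) and 4 to 6% (Wilcoxon), which is no more than chance.

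**What a proportion would show.** Exact (Clopper-Pearson) 95% intervals:
- 1/86 = 1.16%, 0.03% to 6.31%
- 0/86 = 0%, upper limit 1 − 0.025^(1/86) = 4.20%
- with only 43 pairs (assumed), 1/43 = 2.3%, 0.06% to 12.3%

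Another paired test would not help: exact McNemar with one discordant pair also gives p = 1.0.

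**The case against.** A reader might infer that the plan would report no change, or conceal an inhibitor that had occurred. The documents do not support that. A p-value of 0.32 is non-significance, not a finding of no change. SAP 6.6, item 6 also prints descriptive statistics, which SAP 5.1 defines to include the maximum, so a high titre would stand in the same output. SAP 6.6, item 1 gives the number, incidence proportion and 95% CI of each adverse event, so an inhibitor recorded as an adverse event would be counted there.

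A reader might also infer that the primary objective is judged by this p-value. It is not: the SAP does not name the test as the primary analysis and makes it conditional on being possible.

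The figures depend on 86 pairs and exact zeros, and neither is assured. Protocol 7.3.2.4 asks for items with abnormal measurements, so unchanged negative pairs may not be in the database; with a single pair the t-test cannot be computed at all.

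All of this stands and limits the point. Three things remain. The conditional wording does not remove the inhibitor row, since the t-test computes normally with one non-zero difference among many pairs. The adverse event route is partial: under Protocol 7.3.2.1 an abnormal result counts as an adverse event only if it meets listed criteria or the investigator or sponsor judges it to be one, and the incidence is taken over the safety analysis set, not over subjects tested. And no plausible noise level tried gives the test any useful sensitivity.

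For urinalysis the point is conditional. The scale is not stated, and none of the figures above concern those items.

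**Conclusion.** The point holds in a limited form. The SAP's rule covers the inhibitor and calls for a p-value that carries almost no information about a new case. With 86 pairs and all other changes zero, one case gives p = 0.32 by t-test or 1.0 by exact Wilcoxon whatever the titre, and significance needs four equal-titre cases by t-test or six cases by Wilcoxon. With assumed noise in the other values the exact figures change, but detection of a single case stays at chance level. The event would still be visible in the maximum and, if so recorded, in the adverse event tables. The defect is a potentially misleading p-value on the event of primary interest, together with the lack of an inhibitor proportion over subjects tested.

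**What to change.** 1. In SAP 6.6, item 6, exclude the factor VIII inhibitor from the paired tests and correct its label in SAP 4.6.
2. Report the number and proportion of subjects changing from negative to positive among those with both a pre-dose and a post-dose inhibitor test, with an exact 95% CI and no p-value.
3. Before that, reconcile the wording around 0.6 BU/mL in the exclusion criterion (Protocol 7.2.2 and 7.7.2; SAP 2.3.2). It links a titre within the normal range and a titre of at least 0.6 as alternatives, and it is not written as an outcome definition, so it cannot yet serve as the positivity cut-off.
4. Confirm that negative inhibitor results are recorded, given the wording of Protocol 7.3.2.4. If they are not, state the denominator actually available.
5. Summarise any urinalysis item recorded on a categorical scale by a shift table, not a paired mean test.
6. Reconcile the scope of SAP 6.6, item 6 with the narrower Protocol 7.7.2.1.

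The cost is SAP wording, one or two tables and a check of the CRF data. If negative results were not captured, the proportion may rest on fewer subjects than hoped.
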